This protocol outlines the principal features of the statistical analysis for this study. A full statistical analysis plan (SAP) has been published on Clinicaltrials.gov alongside this protocol and prior to the completion of patient recruitment (September 25, 2024).

Participant characteristics

Patient: Group characteristics will be presented using descriptive statistics. Baseline analysis between the intervention and control groups will be conducted to ensure the comparability of the groups.

Physiotherapist participants: Group characteristics (age, sex, department, highest educational level, number of years of clinical experience, adherence to protocol) will be presented using descriptive statistics.

Analysis of primary outcomes

Magnitude of within and between-group change on primary outcomes from baseline to 24-72 hours prior to the initial physiotherapy consultation, 24 hours post initial physiotherapy consultation and three months post-baseline will be analysed through mixed models. Data will be compared based on the 'intention to treat' (ITT) principle. Sensitivity analyses applying per-protocol, complier average causal effect (CACE) analyses and analyses applying study specific MCID associated with dichotomised anchor response on the GRoC will be explored. Sensitivity analyses to adjust for all measured baseline covariates will also be performed to investigate the presence of equipoise as the result of randomisation (Thabane et al., 2013).

Multiplicity/ type I (a) error

The outcomes collected in the study are considered as separate entities and, therefore, restrictive multiplicity penalisation of the model is not required (Dmitrienko & D'Agostino 2013). Adjustment will be used for repeated measures over time for separate test conditions.

Analysis of secondary outcomes

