- More positive and concordant patient and physiotherapist evaluations of MSKP-related shared understanding, communication, participation, involvement and emotional support at the initial physiotherapy consultation.

2. Improvements in MSKP illness perceptions and higher levels of reassurance of the benign nature of MSKP mediate improved pain intensity and pain self-efficacy as a result of exposure to the PainSMART-strategy compared to usual physiotherapy management alone.

The null hypothesis (H0) is that there is no clinically or statistically significant differences between the intervention (film) group and the control group (usual physiotherapy management).

Secondary exploratory research questions

1. What baseline factors are predictive of improved patient outcomes after exposure to the PainSMART-strategy?
2. What baseline factors are predictive of the persistence of MSKP?
3. What type of psychological factors and strategies are associated with patient outcomes after exposure to the PainSMART-strategy?
4. Is pain self-efficacy a potential mediator of the PainSMART-strategy's effect on health outcomes?
5. What are patients and physiotherapists experiences of the PainSMART-strategy?

Study Methods

Trial design

This is a two-armed, parallel group, randomised controlled trial in which the intervention group (PainSMART-strategy + usual physiotherapy management) will be compared to a control group (usual physiotherapy management). Treatment allocation is a 1:1 ratio. The control group and statistician will be blinded. One independent statistician will be blinded for the primary analyses. Another independent statistician will be responsible for database development and linkage of patient and physiotherapist data. The PainSMART-strategy is described in full in the trial protocol.

Randomisation

A computerised randomisation sequence for 800 patients into group A (Intervention group) or B (Control group) has been generated by a blinded statistician using SPSS prior to the start of patient recruitment. Participating patients will be allocated to intervention or control group based on the order of their inception to the study. The randomisation is described in full in the trial protocol.

Framework

The trial's hypotheses apply a superiority testing framework where the PainSMART-strategy is hypothesized to be superior in outcome compared to control.

Determination of Sample size

The sample size calculation is described in full in the trial protocol.

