- Previous healthcare interventions for the actual presenting complaint in the last three months
- Previous healthcare interventions for other MSKP sites in the last three months

- Analgesic medication use (type and consumption)
- Number of comorbidities
- Risk for future work-related disability – low or high risk according to score on Örebro musculoskeletal pain screening questionnaire (ÖMPSQ), where >50 is classified as high-risk.
- Average waiting time to initial physiotherapy consultation

Baseline PROM scores

- Pain intensity with numerical rating scales (NRS).
 - o Worst pain in the last 24 hours (0-10).
 - o Best pain in the last 24 hours (0-10).
 - o Average pain in the last 24 hours (0-10).
- Pain self-efficacy - Pain self-efficacy questionnaire (PSEQ-10; max score 60).
- Traditional pain coping - Brief Pain Coping Inventory (BPCI-2) traditional pain coping subscale (max score 56).
- Psychological flexibility in pain - BPCI-2 psychological flexibility subscale (max score 49).
- MSKP illness perceptions - Brief Illness Perception Questionnaire (BIPQ; max score 80).
- Level of concern as to the potential likelihood of MSKP being caused by a serious pathology - Single question rated on a NRS (0-10).
- Self-reported physical activity in the past week based on three questions
 - o Moderate to intensive exercise (minutes)
 - o Other physical activity beside exercise (minutes)
 - o Sitting time (minutes during a regular day)

Physiotherapists will be described with respect to age, sex, level of education and number of years working as a physiotherapist. Data will be presented for the whole cohort of physiotherapists and separately for the physiotherapists providing treatment in the two randomised groups.

Normally distributed continuous data will be summarised by mean, standard deviations (SD). For non-normally distributed continuous data, median and lower, upper quartile range, will be provided unless otherwise stated. Categorical data will be summarised by number and percentages. Tests of statistical significance will be undertaken for screening of imbalance between groups in baseline characteristics.

Analysis

Time frame for data collection

Primary and secondary patient reported outcome measures (PROMs) will be collected at four time points:

1. Baseline: the same day as initial triage.
2. 24 -72 hours prior to the initial physiotherapy consultation.
3. 24 hours post the initial physiotherapy consultation (primary time point one).

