An internal pilot interim analysis was planned and conducted after 50% of the sample had reported outcomes at time point 2 (pre physiotherapy consultation) and 3 (primary time point one, post initial physiotherapy consultation). This to evaluate the viability of the a-priori sample size calculation and the recruitment frequency. The analysis utilised linear mixed models to investigate between group difference (effect size) for change from baseline to time points 2 and 3 in outcome. The significance level for the interim analysis was $p=0.05$. After interim sample size calculation, the sample size was slightly adjusted when taking loss to follow-up into account. The sample size calculation is described in the trial protocol. The trial would have been stopped if the internal pilot interim analysis could not be performed due to not attaining 50% of the sample size at Time point 2 and 3 within 6 months. No further interim analyses are planned.

Final analysis

The trial is planned to finish recruitment of new patient participants in Dec 2024 – Jan 2025. The final three-month follow-up data collection will therefore be in Mar - Apr 2025. All outcomes will be analysed collectively.

Analysis methods

Primary outcome analysis

-Pain intensity and Pain self-efficacy

Hypothesis testing for the two primary outcomes *pain intensity* and *pain self-efficacy* (score on average pain NRS in the last 24 hours and PSEQ-10) will be based on analysis of group mean change from baseline. Baseline scores and group mean change in primary outcome scores from baseline to primary time points one and two for the intervention and control groups and the between-group change for these time points will be presented as means and CI. The within and between-group change on primary outcomes from baseline to 24 hours post initial physiotherapy consultation and three months post-baseline will be analysed according to ITT principles using a maximum likelihood approach for mixed models adjusted for a relevant covariance structure. The models will be adjusted for baseline covariates where relevant. Baseline factors that will be analysed for potential covariate adjustment include: age, sex, educational level, employment, pain duration, number of pain sites, comorbidities, days to initial physiotherapy consultation, previous healthcare interventions, ÖMPSQ risk category, self-reported sick leave and analgesic medication consumption.

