Patients receive seven questions and physiotherapists 3 questions regarding their experience of the initial physiotherapy consultation. Between group mean difference for responses to these questions will be analysed using independent sample t-tests. These analyses will be presented as mean and SD for each group and the between group difference in mean and CI. Three of the patient questions will be analysed for concordance with the matched physiotherapists' questions. Concordance within the intervention group and control group will primarily be analyzed by calculating intraclass correlation coefficient (ICC) with 95% confidence interval on each question as well as all three questions combined. Two-way random effects model will be used for ICC, assuming raters to be randomly selected. The ratings are single measures analyzed for consistency, to measure systematic differences between ratings. Patients and physiotherapists are treated as two independent raters, rating each of the three questions.

Sensitivity analyses

The following are all re-analyses of the primary and secondary outcomes under different conditions:

- Per-protocol analysis
- Complier average causal effect (CACE) analysis
- Responder analysis
- Complete case analysis (in case of >5% missing data)

Per-protocol analysis

Per-protocol analyses for the primary and secondary outcomes will be conducted to assess robustness of the ITT analyses and to further inform decisions regarding superiority. The sample of the patients for the per-protocol analyses will be as follows:

- Intervention group: patients receiving the PainSMART-strategy with no or minor deviation from protocol.
- Control group: patients receiving intervention with no or minor deviation from protocol.

Data on the physiotherapists' self-reported adherence to the protocol will be cross-referenced with the intervention respective control group patient consultations that each physiotherapist has conducted. This, in combination with the intervention group patients' self-reported exposure to the film, will provide data on deviation from protocol.

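### Neither document fixes the covariates of the primary model: the protocol mentions adjustment only as a sensitivity analysis, and the SAP puts it in the primary model without a selection rule

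*SAP*

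**What the plan says.** **Protocol, Analysis of primary outcomes.** Change from baseline up to "three months post-baseline will be analysed through mixed models" under intention to treat. No covariates are named. Adjustment appears only afterwards: "Sensitivity analyses to adjust for all measured baseline covariates will also be performed to investigate the presence of equipoise as the result of randomisation". The section on secondary outcomes repeats this.

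**SAP, Primary outcome analysis.** The primary analysis is a maximum likelihood mixed model of change from baseline. Then: "The models will be adjusted for baseline covariates where relevant". The candidate list follows: "Baseline factors that will be analysed for potential covariate adjustment include: age, sex, educational level, employment, pain duration, number of pain sites", and further comorbidities, days to the initial consultation, previous healthcare interventions, ÖMPSQ risk category, sick leave and analgesic consumption. That makes twelve factors. The same text recurs for secondary PROMs, register outcomes, and the per-protocol and CACE analyses.

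**SAP, Sensitivity analyses.** The list is introduced by "The following are all re-analyses of the primary and secondary outcomes under different conditions" and has four entries: per-protocol, CACE, responder and complete case. The protocol's all-covariate analysis is not there.

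**SAP, Demography and baseline characteristics.** "Tests of statistical significance will be undertaken for screening of imbalance between groups in baseline characteristics". No threshold is given, and no use for the result.

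**SAP, Trial design.** "One independent statistician will be blinded for the primary analyses". The protocol's Blinding section extends this to the researchers who analyse outcomes collected from both groups.

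**The concern.** A confirmatory analysis needs one model, fixed before anyone can see how the choice affects the answer. Here the role of adjustment differs between the documents, the word that governs it in the SAP is undefined, and neither document says which estimate is primary if the adjusted and unadjusted results disagree. With twelve factors, each in or out, there are 2^12 = 4096 possible covariate sets, and the list is worded so that it may not be closed.

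The order of events adds some weight. Between-group effects at time points 2 and 3 were estimated at the interim analysis on 29 February 2024. Recruitment paused on 21 May 2024 with baseline data complete for 450 patients. The protocol dates the SAP to 25 September 2024, and the SAP still leaves the model open.

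Two things are at stake: the type I error if the model is chosen by its result, and precision. The strongest predictor of a follow-up score is usually the same score at baseline. The SAP uses it in the CACE and mediation models but does not name it among the candidates for the primary model.

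**Working it through.** **1. Role of adjustment, side by side**

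| | Protocol | SAP |
|---|---|---|
| Primary model | Mixed model, no covariates named | Mixed model, adjusted where relevant |
| Covariate set | All measured baseline covariates | A selection from twelve named candidates |
| Role of adjustment | Sensitivity analysis | Part of the primary analysis |
| Selection rule | Not needed | None stated |
| Adjusted sensitivity analysis | Yes | Not listed |

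The mediation models show that a rule was feasible: they have a fixed minimum adjustment set plus the baseline mediator and outcome.

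**2. Type I error if the choice follows the result**

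Inputs from the documents: one-sided α = 0.05 (SAP, Confidence intervals and P values), 408 patients allocated 1:1 (Protocol, Sample size and Trial design) and twelve candidates. Assumed, because the documents give no figure: the joint R² of the covariates with the change score, from 0.05 to 0.50.

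Closed form: under the null, the unadjusted and fully adjusted test statistics correlate at about √(1 − R²) in large samples. Rejecting when either exceeds 1.645 has probability 1 − Φ₂(1.645, 1.645; √(1 − R²)), where Φ₂ is the bivariate normal distribution function.

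Simulation: 4000 null trials per setting, normal covariates with pairwise correlation 0.2, one endpoint and one time point. The Monte Carlo standard error is √(0.05 × 0.95 / 4000) = 0.34 percentage points.

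| R² | Unadjusted | All twelve | Only factors imbalanced at p < 0.05 | Smaller p of unadjusted and all twelve | Same, closed form |
|---|---|---|---|---|---|
| 0.05 | 4.98% | 4.90% | 4.65% | 6.22% | 5.92% |
| 0.10 | 5.08% | 4.90% | 4.55% | 6.60% | 6.31% |
| 0.20 | 4.98% | 4.90% | 4.40% | 6.90% | 6.86% |
| 0.30 | 5.15% | 4.90% | 4.15% | 7.35% | 7.29% |
| 0.50 | 5.22% | 4.90% | 3.48% | 8.05% | 8.01% |

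Either model fixed in advance reproduces the plan's 5%. Choosing between the two by result gives about 6% to 8%. Adjusting mechanically for imbalanced factors does not inflate the error.

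**3. Precision from the baseline score**

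Take equal variance σ² at baseline and follow-up, correlation ρ and complete data. The change score has variance 2σ²(1 − ρ). The follow-up score adjusted for baseline has residual variance σ²(1 − ρ²). The ratio is (1 − ρ²) / [2(1 − ρ)] = (1 + ρ)/2.

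- ρ = 0.3: 1.3/2 = 0.65, a 35% reduction.
- ρ = 0.5: 1.5/2 = 0.75, a 25% reduction.
- ρ = 0.7: 1.7/2 = 0.85, a 15% reduction.

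The values of ρ are assumptions; the documents give none.

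**4. One candidate that is not clearly a baseline factor**

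Patients are randomised once they agree to share contact details (Protocol, Allocation and sequence generation). The interval to the consultation then varies with prioritisation and access (Protocol, Where and how). Patients who cancel stay in the PROM analysis (Protocol, Missing data) but may have no such value. The SAP does not say whether the booked or the actual interval is meant. The actual interval is realised after randomisation.

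**The case against.** The strongest reply is that the documents can be read together. The protocol says that it gives only the principal features and refers to the SAP for the rest. It never states that the primary model is unadjusted; that is implied by where adjustment is placed. The SAP restricts the choice to a named list, and the primary analysis is done by a blinded statistician. All of this stands, and it means that the result could be chosen, not that it will be. But blinding is not a rule, and both documents print the key (A is intervention, B is control), so it protects only if the analysis file carries other codes. Reading the documents together also does not restore the missing sensitivity analysis or define relevance.

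A reader might infer three stronger points.

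- *The imbalance tests choose the covariates.* Neither document says so. The tests stand in the section on baseline description, and the primary analysis section does not refer to them. The candidates could equally be screened for association with outcome. Even if imbalance did decide, step 2 shows no inflation. The objection to such tests would be that they ignore prognostic strength.
- *The documents state two contradictory primary models.* They imply different ones; the protocol's wording is too open for more.
- *The error rate could reach 9% or more.* That takes a search over many models. Taking the best of five plausible models gave 6.6% to 9.5%, and a stepwise search for the most favourable p-value gave 9.0% to 27.7%. Neither document proposes either.

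**Conclusion.** The point holds in a limited form. The protocol mentions adjustment only as an all-covariate sensitivity analysis, the SAP moves it into the primary model without a rule, and the SAP's sensitivity list drops the protocol's analysis. So neither document fixes which estimate is primary.

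The realistic exposure is a one-sided type I error of about 6% to 8% in place of 5%, and only if the unadjusted or twelve-factor model is chosen after both results are known. This rests on an assumed R² of 0.05 to 0.50 and a simplified setting with one endpoint at one time point. Leaving the baseline score unspecified puts a further gain at risk: 15% to 35% less variance than a change-score comparison, for assumed correlations of 0.7 down to 0.3. This should be corrected before unblinding. It does not show that any result has been or will be selected.

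**What to change.** Before unblinding:

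1. State one primary model in both documents: arm, time, arm-by-time and the outcome's baseline score as a covariate, with follow-up scores as the response. A mixed model with baseline in the response and baseline means constrained equal between arms is equivalent in purpose, and within-group change can still be reported from it.
2. If prognostic factors are wanted in that model, list a fixed set of pre-randomisation covariates chosen for prognostic value, and remove the phrase that leaves adjustment to relevance.
3. Name the model with all baseline covariates as the single adjusted sensitivity analysis and add it to the SAP's list, so that it matches the protocol.
4. Leave days to the initial consultation out of the primary model.
5. Delete the significance tests of baseline characteristics, or state that they do not drive adjustment.

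The cost is a few sentences in each document and no new data, since the baseline scores are already collected. The sponsor gives up the discretion to add covariates later. If prognostic factors are kept out of the primary model, some precision is forgone; a fixed adjusted model avoids that and holds the error rate equally well (4.9% in step 2).

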Self-reported analgesic medication use (type and level of consumption) for the presenting MSKP complaint will be collected via two questions. The first question establishes analgesic consumption with three response options: 1. Yes, on a regular basis; 2. Yes, sometimes; or 3. No. The second question establishes the type of analgesic consumption via six response options: 1. Paracetamol, 2. NSAIDs, 3. Opioids, 4. Gabapentinoids/Tricyclic antidepressants/Serotonin-norepinephrine reuptake inhibitors, 5. Don't know, 6. Other (with free text answer).

- *Self-reported sick leave*

Patients will self-report if they are currently on sick leave for their presenting MSKP complaint at baseline, 24-72 hours prior to their initial physiotherapy consultation, 24 hours post-initial consultation and three months post-baseline. Self-reported current sick leave for the presenting MSKP complaint will be collected via one question with the response alternatives: Yes or No.

- *Self-reported healthcare visits*

Self-reported healthcare visits for the presenting MSKP complaint or other MSKP complaints will be collected at baseline relating to the three months prior to baseline. At all other data collection time points, additional healthcare visits for the presenting MSKP complaint will be self-reported. Additional healthcare visits (aside from the study physiotherapist) will be self-reported as yes/no and for which professions the patient has consulted (five options; 1. Physician, 2. Nurse, 3. Another physiotherapist, 4. Chiropractor/Naprapath, 5. Councillor/psychotherapist).

- *Healthcare register data*

Data on participating patient's healthcare consumption, sick leave days, referral for diagnostic imaging and referral to specialist/tertiary care for MSKP during the study period (from baseline to three months) will be collected from RÖ's and RJL's healthcare data registers and the national social security database (Försäkringskassan) following completion of all PROMs and PREMs data collection.

Direct healthcare costs for MSKP per patient during the three-month study period will be collected (Sveriges Kommuner of Regioner, 2020). For all healthcare register data, a comparison will be made between the intervention and control groups to establish if the PainSMART-strategy can improve health outcomes and the effectiveness of the physiotherapy management pathway.

- *Screening tool*

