Physical activity in the past week will be measured using three screening questions developed for the Swedish national board of health and welfare.

1. Self-reported physical activity in the past week regarding moderate to intensive exercise (minutes)
2. Other physical activity beside exercise (minutes)
3. Sitting time (minutes during a regular day)
 - Time Frame: collected at baseline, 24 -72 hours prior to the initial physiotherapy consultation, 24 hours post initial physiotherapy consultation and at three months post-baseline.
 - Calculation to derive outcome:
 - Within and between group mean change in the scores over time from baseline to follow-up three months post-baseline (all time points). Scores on question regarding “Moderate to intensive exercise” and “Other physical activity beside exercise” will also be converted to activity minutes per week < 150min/w or \geq 150min/w.

-Global rating of change

Global rating of change will be measured using a single item Global Rating of Change Scale (GRoCs) scored on an 11-point scale from minus five to plus five, anchored by the terms very much worse (minus five), unchanged (zero) and completely recovered (plus five). The score is based on the period from when the patient first contacted the physiotherapy department to initiate triage until the data collection points for the GRoCs.

- Time Frame: collected at 24 -72 hours prior to the initial physiotherapy consultation, 24 hours post initial physiotherapy consultation and at three months post-baseline.
- Calculation to derive outcome:
 - The score will be dichotomized into improved (1-5) and unchanged/worse (-5-0).

-Analgesic medication use

Self-reported analgesic medication use (type and consumption) for the presenting MSKP complaint will be established via two questions. The first question establishes self-reported consumption of analgesics with the answer alternatives: Yes, on a regular basis; Yes, sometimes; or No. The second question establishes the type of analgesics taken for MSKP and is ranked according to the analgesics ladder recommendations from the Östergötland health care region pharmaceutical committee (2024) (1. Paracetamol, 2. NSAID, 3. Opioids/gabapentinoids/Tricyclic antidepressants/Serotonin-norepinephrine reuptake inhibitors).

- Time Frame: collected at baseline, 24 -72 hours prior to the initial physiotherapy consultation, 24 hours post initial physiotherapy consultation and at three months post-baseline.

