The study specific MCIDs for secondary outcomes at all time points will be calculated for interpretation of the within and between-group differences. The MCIDs will be calculated for the whole cohort using an anchor method (Revicki et al., 2008). A dichotomised anchor response on the GRoC (-5- 0 = not improved; 1-5 = improved) must at least have a small association with change in the secondary outcome from baseline to all time points. This will be applied in a ROC curve analysing the AUC, specificity, sensitivity and Youden index to attain an optimal cut of point for the MCIDs. MCIDs will be presented in mean and SD.

-Categorical variables

Hypothesis testing for secondary dichotomous outcomes for *Global rating of change*, *fulfilment of physical activity recommendation*, *analgesic medication consumption*, *self-reported sick leave* and *self-reported healthcare visits* will be based on analysis on differences in proportions over time using generalised linear mixed models. For the secondary multinomial outcome regarding *type of analgesic medications* (1. Paracetamol, 2. NSAID, 3. Opioids/gabapentinoids/Tricyclic antidepressants/Serotonin-norepinephrine reuptake inhibitors) differences in proportions over time will be analysed using generalised logit mixed models. The numbers and proportions for secondary dichotomous outcomes will be reported at all relevant time points for the intervention and control groups as well as between-group comparisons for all time points presented as odds ratio and CI.

Healthcare register outcome analyses

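### The analgesic-type model has no level for patients taking none, so as written its follow-up proportions are among users only; the cut for the three-answer consumption item is also unstated

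*SAP*

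**What the plan says.** Two questions are asked. On consumption, the protocol (Self-reported analgesic use) states: "The first question establishes analgesic consumption with three response options: 1. Yes, on a regular basis; 2. Yes, sometimes; or 3. No". The SAP (Outcome definitions, Analgesic medication use) keeps the same three answers. On type, the protocol states: "The second question establishes the type of analgesic consumption via six response options". Those six include a don't-know answer and a free-text other; none of them means no analgesic. The SAP reduces type to three classes: "The second question establishes the type of analgesics taken for MSKP and is ranked according to the analgesics ladder recommendations".

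The SAP's Categorical variables section then places consumption in the list that opens "Hypothesis testing for secondary dichotomous outcomes for", to be analysed with generalised linear mixed models, and gives no cut. For type it names those three classes as the only levels and says that "differences in proportions over time will be analysed using generalised logit mixed models".

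Three other places bear on this. The SAP's outcome definition promises numbers and proportions for consumption and type in each group, without a denominator or a rule for non-users. Statistical analysis population defines ITT as all randomised patients. The confirmatory hypotheses include lower analgesic use under the intervention.

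**The concern.** A patient who takes nothing at a visit fits none of the three classes. If that patient has no value, drug type is compared only among those still using analgesics. Who is still a user at follow-up may depend on the film, so the two user groups are no longer the groups that randomisation made comparable. If the film leads users of class 1 drugs to stop, those who remain in the intervention arm will include a larger share on class 3 drugs even though nobody moved up the ladder. A favourable change could then be read as a shift to stronger drugs.

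The consumption item has a smaller gap. Three answers must become two, and the SAP does not say where to split them, although it does state the split for global rating of change and for physical activity. Until it is fixed, the choice could be made after the data are seen.

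**Working it through.** The documents give no analgesic use rates and no figure for these outcomes, so there is nothing to reproduce. The rates below are assumptions; the levels, model and population come from the sections cited above.

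**1. Who has a value.** The model has levels 1, 2 and 3. A patient answering No on consumption matches none of them. Treating such patients as missing does not solve this: the SAP's Missing data section works under missing at random, which would imply a drug class for people who took no drug.

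**2. Single example.** The only true change is 12 points moving from class 1 to none.

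| Arm | None | Class 1 | Class 2 | Class 3 |
|---|---|---|---|---|
| Control | 40% | 30% | 20% | 10% |
| Film | 52% | 18% | 20% | 10% |

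- Class 3 among all randomised: 10% v 10%.
- Class 3 among users: control 0.10/0.60 = 16.7%; film 0.10/0.48 = 20.8%.

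**3. Range.** Assume control users split 50/33/17% across classes 1/2/3. Let u be the proportion of control patients who use any analgesic, and s the proportion of the film arm that stops class 1 drugs. Class 3 among all randomised is 0.17u in both arms. Among users it is 17.0% in control and 0.17u/(u − s) with the film.

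| Control non-users | Class 3, all randomised (both arms) | Class 3 among film users, s = 5 / 10 / 15 points |
|---|---|---|
| 20% | 13.6% | 18.1 / 19.4 / 20.9% |
| 40% | 10.2% | 18.5 / 20.4 / 22.7% |
| 60% | 6.8% | 19.4 / 22.7 / 27.2% |

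**4. What adding none changes in the example.** Odds ratios, film v control:

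- Class 3 v class 1: (0.10/0.18)/(0.10/0.30) = 1.67, with or without the extra level.
- Class 3 v none: (0.10/0.52)/(0.10/0.40) = 0.77. Only available with the extra level.
- Class 1 v none: (0.18/0.52)/(0.30/0.40) = 0.46. Only available with the extra level.

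So the extra level does not alter the contrast between two drug classes. It supplies proportions of all randomised patients and the contrasts that show what happened: fewer patients on class 1 drugs, more on none.

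**5. Would an ordinal model serve better?** Cumulative odds ratios in the same example:

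- Any use: (0.48/0.52)/(0.60/0.40) = 0.62.
- Class 2 or higher: 30% v 30%, so 1.00.
- Class 3: 10% v 10%, so 1.00.

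Proportional odds fails in the very scenario that motivates the point.

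**6. The consumption cut.** Assume 60% any use in both arms and 10 points moving from regular to sometimes with the film.

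- Any v none: odds ratio 1.00.
- Regular v rest, 20% to 10%: (0.10/0.90)/(0.20/0.80) = 0.44.
- Regular v rest, 30% to 20%: (0.20/0.80)/(0.30/0.70) = 0.58.

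The same data show no effect or a clear one, depending on the cut.

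**The case against.** The best reply is that no sentence in the SAP excludes non-users. The proportions are described for each group at each time point, the population is all randomised patients, and the consumption answer already identifies who takes nothing. That stands as far as it goes: users only is what the listed levels imply, not a stated rule. A reader might infer that the authors chose a users-only comparison, and the documents do not show that. But the model has no level in which to put non-users, so the reply does not remove the problem.

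A second reply is that the hypothesis concerns lower use, not drug type, and that consumption is tested separately. With a cut at any v none, patients who stop would count as a benefit there. This limits the harm but depends on a cut the SAP does not state, and type is still tested as an outcome of its own.

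A third reply is that reducing three answers to two is legitimate, and that a generalised logit is valid for ranked classes. Both stand. The gap in consumption is the missing cut. As for type, a reader might infer that the model is wrong because it ignores the ladder ranking; it is not, and it avoids the proportional-odds assumption that fails in step 5.

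**Conclusion.** The point holds as a cheap improvement to secondary outcomes. As written, the type model gives non-users no value, so its follow-up proportions describe a group selected after randomisation. Under the assumptions shown, identical class 3 use in the randomised arms appears as 17.0% v 18.1% to 27.2% among users (16.7% v 20.8% in the single example). The direction rests on stoppers coming from class 1; the size rests on assumed rates, because the documents give none.

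A reader might take the odds ratio of 1.67 for class 3 v class 1 as the bias caused by omitting none. It is not: it is the same with none included. The SAP also promises odds ratios explicitly only for the dichotomous outcomes.

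The selection problem concerns follow-up visits only, because baseline answers precede access to the film. The primary outcomes and their conclusions are untouched.

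**What to change.** In the SAP's analgesic outcome definition and its Categorical variables section:

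- Code type as 0 = none (consumption answered No) plus the three existing classes. Keep the generalised logit mixed model, with none as the reference, and include all randomised patients.
- Give the don't-know and other answers, which the protocol collects but the SAP's classes omit, an explicit nominal category.
- State the rule for patients who report several types. The ranking hints at the highest class, but neither document says so, nor whether several answers are allowed.
- State the cut for consumption, for example any v none, which matches the hypothesis of lower use, and report all three levels descriptively.
- Treat a cumulative-logit model as optional only.

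The cost is a few lines of SAP text and no new data, since the consumption question already identifies non-users. The downside is one or two more categories, possibly sparse. The change should be made and dated before group-level results for these outcomes are seen.
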